BMI is a widely used as an index of nutritional problems. In a meta-analysis which included 2.88 million people, the optimal BMI for overall survival was found to be 25-30 kg/m² (Flegal, 2013; Dixon, 2014 ; Pan, 2012). Rapid weight loss is a strong indicator for health and functional decline. Such a weight loss, especially with low BMI values, usually mandates investigation in order to eliminate the cause or to limit its effect. A use of an automatic e-mail alert system was found to improve screening rate of malnourished patients in hospital (Giovannelli, 2014).

Correlation between death and HbA1c% is U-shaped, with increased mortality under a 6.5% level in patients taking two antidiabetic medicines (Currie, 2010). Among these patients, the optimal HbA1c% values of for survival were 7.5-8%. A substantial proportion of older adults with diabetes were found by Lipska et al. (2015) to be potentially overtreated.

Correlation between death and cholesterol is also U-shaped (Iso, 1989). Hypocholesterolemia is defined as cholesterol below 160 mg% and predicts increased mortality and morbidity (Hazzard's, p. 1341). We found no interventional study for this situation in the scientific literature.

In our experience, Email alerts to doctors, regarding an over-tight control of specified diabetic patients by sulphonyl-urea medicines was followed by a reduction (from 3% to 1.8%) in

mortality comparing to a previous-year matched control group (unpublished observations). While this result was not statistically significant, it encouraged us to try this large scale interventional clinical trial. It also served us in assessing the size of the study population needed.

Objectives:

This study aims to determine whether reminding physicians and nurses about too low values of weight (as BMI), glucose (as HbA1c%) or cholesterol (as total serum cholesterol) improves survival and health of people older than 75 years.

Study Hypotheses:

A. Main Study Hypotheses:

1. Compliance: Sending the intervention letter will cause a positive change in the relevant index (a rise in BMI, HbA1c%, or cholesterol, respectively).
2. Health effect: Sending the intervention letter will cause a lower mortality rate in each study group compared to control groups, within a year.

B. Other Study Hypotheses: compared to control groups, sending the intervention letter will cause improvement in morbidity and in secondary measures (see below).

And in detail:

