Reducing numbers of hospital stays and days of stays, numbers of physician and nurse visits with records of symptoms, number of dispensed medicines, medical expenses; in the HbA1c% intervention - reduced number of dispensed anti-diabetes medicines and reduced rate of measuring glucose levels of 70 mg/dL or less ; in the cholesterol intervention - reduced number of dispensed anti-cholesterol medicines.

Increasing rate of weight measuring, BMI level, HbA1c% measuring, HbA1c% level, cholesterol measuring, cholesterol level; in the BMI intervention - percentage of patients evaluated by a nurse and counseled by a dietician.

Methodology:

Briefly: This prospective, randomized controlled trial, will compare BMI, HbA1c% and cholesterol values, rate of death, number of stays, days of stays, numbers of physician and nurse visits with records of symptoms such as "weakness", "dizziness" and total medical expenses of patients 75 years and older that their clinic staff will receive the email concerning them, versus patients that such email concerning them will not be sent. The trial has 3 different alerts: 1. An alert about a significant drop in BMI; 2. An alert about low HbA1c% level in patients treated with diabetes medicines; and 3. An alert about hypocholesterolemia in patients treated with cholesterol-lowering medicines.

Recruiting and inclusion criteria: 75 years and older at the beginning of the trial, clients of Clalit health Services at the North and the South districts, which will be identified thru the computer system (BO) as having one or more of the following:

For alert no. 1: A drop in BMI of 2 Kg/m² or more during the last two years and¹ a BMI lower than 23 Kg/m² and¹ no dietician counseling during the last year.

For alert no. 2: HbA1c% of 6.5% or less and¹ dispensing diabetes medicines during the last 2 months.

For alert no. 3: Total cholesterol less than 160 mg/dL and¹ dispensing cholesterol-lowering medicines during the last 2 months.

Exclusion criteria:

General: Clients that an email address of their physician or nurse is not found.

For alert no. 3: Clients with a diagnosis of myocardial infarction, ischemic heart disease, transient ischemic attack or cortical cerebrovascular accident.

Study schedule:

Sending the alerting mails will be done in one-session during 2015.

Collecting the data will be done after one year.

Publishing the main results will be done within another year at the latest (2017).

Study procedures and methods:

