0. Preparations:

A pre-trial email will be sent to the primary physicians on behalf of the district managements in order to inform about the trial. The text is provided in appendix No. 4. Feedback regarding receiving of the letter (full email boxes etc.) will be collected. Primary physicians would be able to choose to refrain from participating.

1. Finding the participants:

A. By using the Clalit health services computer system; an Excel table will be created; which will include these fields: Identity number; Name; Age; Sex; Clinic name; Primary physician name; Primary physician's email address; Nurse in charge at the clinic; email address of that nurse; Last BMI value of the last year; First BMI value of the previous year; Existence of a dietician visit on the last year; Last total cholesterol level; Whether dispensing of a cholesterol lowering medicine was recorded during the last 2 months; Name of (the last) cholesterol lowering medicine dispensed - with dose and quantity; Whether dispensing of a diabetes medicine was recorded during the last 2 months;

¹ AND as intersection

Name of (the last) diabetes medicine dispensed - with dose and quantity; Whether diagnosed with myocardial infarction; Whether diagnosed with brain infarction; Whether diagnosed with any cardiovascular disease.

B. Participants for each separate inclusion group, according to the criteria above, will be identified. At this stage, a new list will be created, where the people who don't fit any of the criteria will be excluded. Some of the participants may fit more than one criterion. Hence 7 subgroups are created:

- A) Patients that fit only alert 1. (Significant weight loss without dietitian assessment)
- B) Patients that fit only alert 2. (A potentially too tight medicinal diabetes treatment)
- C) Patients that fit only alert 3. (A potentially too tight medicinal cholesterol lowering)
- D) Patients that fit both alert 1. and alert 2.
- E) Patients that fit both alert 1. and alert 3.
- F) Patients that fit both alert 2. and alert 3.
- G) Patients that fit all alerts: 1. , 2. and 3.

C. Population size: According to 11.2014 there are about 5000 patients that fit these criteria at North district and a similar number at the South district, totaling ~ 10,000. This provides a sufficient statistical power to examine the effect on the main hypotheses. (We used Pearson χ^2 test, assuming a 3% to 1.8% decline in death rates, as observed in a similar setting).

2. Randomization:

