- a. Randomization aims to get an unbiased and equal division into an intervention group and a control group.
- b. Randomization will be via computer: by adding a column in the excel table, with the function =ROUND(RAND(),0). This means 1:1 randomization to 0 (control) or 1 (intervention letter).
- c. In order to avoid large differences in numbers of participants among the subgroups, the randomization procedure will repeat until the difference between control and intervention group is less than 2%.

3. The alert emails will be prepared and sent via "Mail Merge" (of Microsoft Word) to the primary physicians and to the nurses in charge at the same clinics. The templates to those emails are shown in the appendix. Technical problems (e.g. full mailbox of recipients) will be recorded and managed promptly (- days, hopefully), by the principal investigator.

4. Collecting outcome data: will be via the Clalit health services computer system. Data will include:

a. For all participants (control and trial groups), for the year that follows the intervention email:

1. Mortality (of any cause)
2. Days in stays (of any ward)
3. Number of stays
4. Number of physician visits
5. Number of nurse visits with symptoms
6. Number of all medicines dispensed
7. Medical expenses
8. Last BMI level and date
9. Last cholesterol level and date
10. Last HbA1c% level and date
11. Glucose levels of 70 mg/dL or less, and dates

b. For alert 1., for the year that follows the intervention email:

1. Recording of functional estimation by a nurse
2. Recording nutritional estimation by a nurse
3. Recording dietitian consultation

c. For alert 2. on the 3 months that follows the intervention email:

1. Whether a diabetes medicine was dispensed, and if so:
2. Name of diabetes medicine, dose and quantity

d. For alert 3. on the 3 months that follows the intervention email:

1. Whether a cholesterol lowering medicine was dispensed, and if so:
2. Name of medicine, dose and quantity

5. Data security: will be handled according to Clalit health systems procedures. The information will be saved in allowed secure servers only and will be available to authorized researchers only after their guidance and signing a non-disclosure commitment. When applicable, personal identification details will be omitted from the lists.

6. Outcome analysis:

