Categorical variables will be shown as frequencies and percentages. Continuous variables will be shown using standard distribution indices (e.g. average, standard deviation, median, etc.). Differences between the arms of the study will be examined using Chi-square test (or Fishers' exact test) for categorical variables and T-test (or Wilcoxon two sample test) for continuous variables. The statistical processing will be performed using Excel or SAS 9.2 software and will be statistically significant if $P < .05$.

7. Ethical issues of the trial:

A waiver of the requirement to obtain a signed informed consent from participants is requested with the following reason: There is no contact with the patients, only unsheathing their existing data.

A waiver of Form 11 is requested with the following reason:

The family physician will be the one who would get the alert related to this trial in the first place.

Appendixes:

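### Main hypothesis A1 can be tested only in re-measured patients, and the plan has no rule for deaths or unmeasured patients although it expects the letter to increase measuring

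*Combined protocol and SAP*

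**What the plan says.** Study Hypotheses, part A, lists two main hypotheses. The first (A1, Compliance) is "Sending the intervention letter will cause a positive change in the relevant index". The second is lower mortality within a year.

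The follow-up data for A1 are entries 8 to 10 of item 4a (Collecting outcome data): "Last BMI level and date", the same for cholesterol, and "Last HbA1c% level and date". They come from the health service's computer system. The section on ethical issues says that patients are not contacted, so no measurement is scheduled by the study.

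Section 6 (Outcome analysis) gives the whole method for such outcomes: "T-test (or Wilcoxon two sample test) for continuous variables", with significance at P < .05. It names no covariate, no analysis set for A1, and no handling of patients who die or have no value. A1 speaks of a change, while the Methodology summary speaks of comparing values. Section 6 does not settle which is tested.

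Hypothesis B lists, among the expected effects of the letter, "Increasing rate of weight measuring, BMI level, HbA1c% measuring, HbA1c% level, cholesterol measuring, cholesterol level".

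On baseline data, the field list in item 1.A includes "Last BMI value of the last year; First BMI value of the previous year" and "Last total cholesterol level; Whether dispensing of a cholesterol lowering medicine was recorded during the last 2 months". It has no HbA1c% value, although alert 2 selects on "HbA1c% of 6.5% or less" and the letter in Appendix 2 has a space for the patient's result.

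**The concern.** Randomisation protects a comparison of everyone randomised. It does not protect a comparison of those who happened to be measured afterwards. The plan's own hypothesis is that more patients will be measured in the alerted arm. If the extra patients have a higher or lower index than the others, the two measured groups differ even when the letter does nothing to the index. Deaths are a second route, because the other main hypothesis is that the letter changes who survives.

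At stake is the reading of one of two main hypotheses. Selective measuring could produce an apparent rise or hide a real one. The planned comparison of measuring rates would show that the arms differ, but nothing says what that does to the A1 conclusion.

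**Working it through.** **The plan's own figures.** There is none for A1. The only sample-size statement (item 1.C) concerns mortality: about 10,000 patients, 3% versus 1.8%. With 5,000 per arm pooled, this gives 97.5% power two-sided, so the statement is consistent for one pooled mortality comparison. It does not cover A1.

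**Inputs.** The documents give no re-measurement rate, SD or alert-group size, so the following are assumptions:
- n = 1,667 per arm, from 10,000 / (3 alerts × 2 arms). The real groups overlap and need not be equal.
- Share measured: pC in control, pA in the alerted arm.
- d: how far the extra patients measured in the alerted arm differ from the rest, in SD of the index.
- No true effect on the index; two-sided test at 1.96.

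**Formulas.** Bias = (pA − pC)/pA × d. SE = √(1/(n·pC) + 1/(n·pA)). Rejection = Φ(−1.96 + bias/SE) + Φ(−1.96 − bias/SE).

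| pC vs pA | d | Bias (SD) | SE | False-positive rate |
|---|---|---|---|---|
| any, measuring unrelated to index | 0 | 0 | – | 5% |
| 90% vs 93% | 0.3 | 0.03/0.93 × 0.3 = 0.010 | 0.036 | 5.8% |
| 85% vs 90% | 0.3 | 0.05/0.90 × 0.3 = 0.017 | 0.037 | 7.3% |
| 60% vs 75% | 0.1 | 0.15/0.75 × 0.1 = 0.020 | 0.042 | 7.6% |
| 60% vs 75% | 0.3 | 0.15/0.75 × 0.3 = 0.060 | 0.042 | 29% |

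At 500 per arm, the last row falls to 12%.

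**A second selection model**, in which measuring depends on a latent variable with correlation ρ to the index, gives 7.0% (|ρ| = 0.1) and 24% (|ρ| = 0.3) at 80% vs 90% and 1,667 per arm. Its biases of 0.0155 and 0.0465 SD correspond to d = 0.0155 × 0.90/0.10 = 0.14 and 0.0465 × 0.90/0.10 = 0.42. The 24% therefore comes from a wider gap and stronger selection than in the 6% to 7% rows.

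**Opposite direction.** At 60% vs 75%, a true rise of 0.10 SD has 65% power (0.10/0.042). A bias of −0.06 SD leaves 0.04 SD and 16% power.

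**Deaths.** If patients kept alive differ by 0.5 SD, 3% vs 1.8% mortality gives 0.012/0.982 × 0.5 = 0.006 SD. Assumed control mortality of 10%, with the same relative reduction, gives 0.04/0.94 × 0.5 = 0.021 SD.

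**What baseline adjustment does.** In a simulation (3,000 runs, 60% vs 75%, d = 0.3, no true effect, baseline–follow-up correlation r = 0.4 to 0.8):
- If measuring depends on the baseline value, the unadjusted test rejects in 29% to 31% of runs. ANCOVA rejects in 5% to 6%, with bias of 0.001 SD or less.
- If measuring depends on something unrecorded, ANCOVA leaves the bias at 0.060 SD and shrinks the SE by √(1 − r²). At r = 0.6 the SE is 0.042 × 0.8 = 0.034, and rejection rises from 29% to 42%. At 85% vs 90% it rises from 7% to 9%.

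**The case against.** Several points on the other side are sound.

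- An unadjusted two-sample test is not biased in a randomised comparison with complete outcomes. This stands. Without differential measuring, adjustment is only a gain in precision.
- The plan may intend a change score, since A1 speaks of change and baseline BMI and cholesterol are extracted. A reader might infer that the plan tests the raw last value and ignores the baseline, but no section says so. The choice is unstated. A change score would still cover only measured patients, so the gap remains.
- Re-measurement may be high. The Background says these indices are part of quality measures, eligibility needs recorded values, and alerts 2 and 3 need recent dispensing. The letters ask for reassessment, not explicitly for a new measurement, and the rise in measuring is only a hypothesis. This supports the lower rows of the table.
- Adjustment is not a cure. Patients are selected on low baseline values, which weakens the baseline–outcome correlation. If an unrestricted r of 0.6 becomes 0.35 to 0.41, power for a 0.10 SD rise at 60% vs 75% is 71% to 73%, against 83% if r = 0.6 held in the selected patients. With unrecorded selection, adjustment makes a false positive more likely.
- The plan already collects measuring rates, dates, dispensing and nurse or dietitian records, and A1 is labelled compliance rather than health effect. These help interpretation but give no rule for A1.

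**Conclusion.** The gap is real and should be closed. A1 can be assessed only in patients whom routine care re-measures, the plan expects the letter to change who is re-measured, and it states no rule for deaths or unmeasured patients. Whether A1 is biased, in which direction and by how much, cannot be derived from the documents.

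Under assumed inputs, with 85% to 93% measured and a 0.3 SD difference, a nominal 5% test becomes about 6% to 7%. A reader might take the 29% figure as the expected error rate, or conclude that A1 will falsely favour the letter. The documents support neither. The 29% needs 60% vs 75% measured as well as selective measuring, and selection can equally hide a real rise.

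The mortality hypothesis is untouched by this, because death is recorded for every randomised patient whether or not the index is measured.

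**What to change.** 1. For each alert, make the A1 analysis a comparison of the follow-up index adjusted for its baseline value (ANCOVA), with age, sex and eligibility subgroup as covariates. Add baseline HbA1c% to the item 1.A fields. Do not carry the baseline forward for unmeasured patients: they were selected for low values, so regression to the mean would favour the arm measured more.
2. Define A1 among patients with a value recorded in the follow-up year, including a value taken before death. Show the share measured and the deaths by arm next to the result.
3. Add one sensitivity analysis for survivors without a value. It shifts the adjusted difference by (share unmeasured, alerted) × δ alerted − (share unmeasured, control) × δ control, over a range justified in advance. Report deaths separately and assign them no index value. The range matters. If the unmeasured were 10% and 15%, opposite shifts of 0.5 SD would move the result by 0.10 × (−0.5) − 0.15 × 0.5 = −0.125 SD, more than a 0.10 SD effect.
4. Read A1 together with the records already planned in items 4b to 4d (nurse, dietitian, dispensing), which do not depend on re-measurement. State that they are taken in both arms.

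The cost is one baseline field, already needed for eligibility and the letter, and modest analysis work. No patient contact is needed. The downside is that adjustment removes only selection linked to recorded baseline data. If measuring depends on unrecorded reasons, the bias stays and the smaller SE makes a false positive somewhat more likely (42% vs 29% in the assumed extreme case, 9% vs 7% at 85% vs 90% measured). The adjusted result must therefore always be reported with the sensitivity analysis.

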CLINICAL TRIAL PROTOCOL

METABOL_EMAIL

ENGLISH VERSION

Electronic mail to clinic team, advising treatment modifications due to low metabolic indexes of 75+ years old patients: Effect on health measures.

Principal Investigator: [name]

Clalit Health Services

[name].

[contact]

Protocol Version #3 13/10/2015

Translated From Hebrew To English

Investigators:

[name], PhD; [name]; [name], MPA, RN; [name], RN ; [name], BSc, MHA ,RD; [name]; [name].

Background:

Technologic progress promotes large scale medical monitoring and intervention. It enables increased attention to signs of nutritional deficiency. Notable examples include the monitoring of Body Mass Index (BMI), glycated hemoglobin (HbA1c%) and total serum cholesterol (herein referred to as cholesterol), which are integrated in the system of quality measures today (e.g. the Israeli National Program for Quality Indicators in Community, 2012). Monitoring and correcting caloric nutritional deficiencies are critical for optimal medical and nursing care, certainly at ages of 75 years and more (Hazzard's, 2009; Brunner & Suddarth's, 2013).

Interactions between diseases, nutritional status and medical treatment are particularly complicated with advancing age. Old age often comes with multiple morbidity as well as increased vulnerability to medicine adverse effects. These may result in nutritional imbalance, which is detrimental to health and to daily living functions. Malnutrition is a major cause of vulnerability to stress (frailty). Intriguingly, medicines that may harm the digestive system and nutritional status include those that are used frequently to improve 'quality indicators'. Examples include metformin, statins and many more.

Hence, when monitoring health quality indicators, the authors believe it is important to search for optimal values - that include minimum levels (and not only maximum levels) for each physiologic indicator. In this trial, we will focus on BMI, HbA1c% and cholesterol.

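### A higher rate of weight, HbA1c% and cholesterol measuring is predicted, but only the last value and its date are collected, so the number of measurements per patient cannot be analysed

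*Combined protocol and SAP*

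**What the plan says.** The detailed list under Study Hypotheses, part B, names these increases expected in the intervention arm: "Increasing rate of weight measuring, BMI level, HbA1c% measuring, HbA1c% level, cholesterol measuring, cholesterol level". Measuring and level are listed as separate outcomes for HbA1c% and cholesterol, and weight measuring stands beside BMI level.

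The data to be extracted are in Study procedures and methods, section 4 (Collecting outcome data), part a, which applies "For all participants (control and trial groups), for the year that follows the intervention email". The entries for the three indexes are "Last BMI level and date" (a.8), "Last cholesterol level and date" (a.9) and "Last HbA1c% level and date" (a.10). No item asks how many times an index was measured.

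Other items in the same list do support counting. Stays, visits and dispensed medicines are collected as numbers, for example "Number of physician visits" (a.4). Low glucose is collected as "Glucose levels of 70 mg/dL or less, and dates" (a.11), that is, every such value with its date.

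Section 6 (Outcome analysis) gives general tests only: chi-square or Fisher for categorical variables, t-test or Wilcoxon for continuous ones. It neither defines a measuring rate nor assigns it a test.

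**The concern.** Three secondary outcomes concern measuring activity, but the extract keeps one record per patient per index. A patient tested five times and a patient tested once look the same if their last tests fall on the same date.

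Measuring is one of the closest links between the letter and any change in care. The letters ask staff to re-assess the patient and the treatment, and a repeat measurement is a natural early response. If mortality and the index levels turn out not to differ, testing frequency would help separate letters that were ignored from letters that were acted on without benefit. An outcome that records only whether any test was done can miss part of that response, most of all where patients are tested several times a year anyway.

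**Working it through.** The plan gives no figure for measuring, so there is none to reproduce. The check has two parts.

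**1. What the listed fields allow**

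| Quantity | From a.8 to a.10? |
|---|---|
| Measured at least once in the year | Yes: a last value dated within the year exists or does not |
| Interval from email to last test | Yes: the emails go out in one session and the last date is kept |
| Number of tests per patient | No |
| Tests per patient-year alive | No |

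**2. What the missing count could cost**

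Inputs from the documents: about 10,000 patients (section 1.C), 1:1 allocation (section 2), significance at P < .05 (section 6; two-sided assumed), one year of follow-up.

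Assumed inputs: m tests per year in controls, from 0.5 to 4; a 10% rise with the letter; 1,650 per arm for one alert. The last is roughly 10,000 / 2 arms / 3 alerts = 1,667. The documents give no size by alert, and the overlap between alerts is ignored.

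Formulas, with n per arm and treated mean 1.1m:
- Poisson: P(at least one) = 1 − exp(−m). Count: z = 0.1m / √(2.1m/n).
- Twofold overdispersion (negative binomial, variance twice the mean in both arms): P(at least one) = 1 − 2^(−m). Count: z = 0.1m / √(2 × 2.1m/n).
- Yes/no power: usual two-proportion normal approximation. Count power: Φ(z − 1.96).

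Worked case, m = 3 with overdispersion:
- Yes/no: 1 − 2^(−3) = 0.875 and 1 − 2^(−3.3) = 0.898. The difference is 0.0235 and its standard error 0.0110, so z = 2.13 and power is about 57%.
- Count: 0.3 / √(2 × 6.3/1650) = 0.3/0.0874 = 3.43, so power is 93%.

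| m per year | Poisson: measured at least once | Power, yes/no v count | Overdispersed: measured at least once | Power, yes/no v count |
|---|---|---|---|---|
| 0.5 | 39.3% → 42.3% | 41% v 51% | 29.3% → 31.7% | 32% v 29% |
| 1 | 63.2% → 66.7% | 56% v 80% | 50.0% → 53.3% | 49% v 51% |
| 2 | 86.5% → 88.9% | 57% v 98% | 75.0% → 78.2% | 59% v 80% |
| 3 | 95.0% → 96.3% | 44% v >99% | 87.5% → 89.8% | 57% v 93% |
| 4 | 98.2% → 98.8% | 29% v >99% | 93.8% → 95.3% | 48% v 98% |

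The overdispersed columns are the fairer comparison, because the extra variation is applied to both measures. They also show that a proportion of 95% at 3 tests a year depends on pure Poisson testing.

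Sensitivity to the form of overdispersion: let the negative binomial shape k = m be the same in both arms. P(at least one) is then 1 − 2^(−m) in controls and 1 − 2.1^(−m) with the letter, and the count variances are 2m and 2.31m. Power for yes/no v count is 28% v 50% at m = 1 and 33% v 92% at m = 3.

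**Two limits on the loss.** With all 5,000 per arm and Poisson testing, the yes/no alone has 96% power at m = 1 and 69% at m = 4. The last date also carries information: at 1,667 per arm under Poisson testing, time since last test gives 60% power at m = 1 and 78% at m = 4, against 56% and 30% for the yes/no.

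**The case against.** The best defence is that the protocol usually means a proportion when it says rate. It speaks of rates for mortality and for screening, and of numbers for stays, visits and medicines. On that reading, the measuring rate is the share of patients measured in the year, and items a.8 to a.10 supply it. This stands. A reader might infer that the rate cannot be computed at all, but the documents do not support that: only the frequency is out of reach.

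A reader might also infer that the yes/no must be close to ceiling, since the Background says of the three indexes "which are integrated in the system of quality measures today" and patients enter through a recorded value. The documents do not support this either. They give no testing frequency. The HbA1c% and cholesterol entry criteria carry no time window for the test. Items a.8 to a.10 also cover all participants, many of whom did not enter through the index in question. A patient who meets only the cholesterol alert need not have had HbA1c% or BMI measured.

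Nor is it right that the timing of the last value relative to the letter is hidden, since both dates are known. Time since last test could even serve as an indirect measure of frequency, but that depends on the testing model, is affected by death, and is not planned.

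Finally, this is one of the other hypotheses, the records are electronic, and the data could be drawn later. That lowers the priority. It does not supply the missing field or the missing definition.

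**Conclusion.** The point holds in a limited form. The plan predicts more measuring of three indexes, does not define the measuring rate, and collects nothing from which the number of measurements per patient can be obtained. The proportion measured at least once and the date of the last test remain available.

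How much is lost depends on a testing frequency that the documents do not give. With twofold overdispersion in both measures, a count is clearly better at 2 or more tests a year (80% v 59% at 2, 93% v 57% at 3) and offers little or nothing at 1 or fewer. With less variation, or another form of it, the count also gains at 1 a year. All these figures rest on the assumed frequency, the 10% rise, 1,650 per arm and the assumed testing distribution. They illustrate the possible loss and do not estimate it for this trial.

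This is a cheap improvement to a secondary process outcome. The mortality comparison is unaffected.

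**What to change.** - Change items a.8 to a.10 to extract every BMI, HbA1c% and cholesterol result, with its date, in the year after the email.
- Define the measuring outcome as the number of results per patient-year alive. Name the analysis: either the Wilcoxon test already in section 6 or a count model that allows for overdispersion and for time alive.
- Report the proportion measured at least once beside it, so that both meanings of rate are covered.
- Take the last level from the same extract, which leaves the level outcomes as they are.

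The source is the same computer system already used for outcomes, and no patient contact is needed. The cost is a larger data file and slightly more analysis, possibly for little gain if testing turns out to be about once a year or less. If the extract is not changed, the plan should at least define the measuring rate as the proportion measured at least once in the year.

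### No pre-email medicine count is listed or used for the alert 2 and alert 3 medicine-count outcomes: a small, cheap loss of precision on secondary outcomes

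*Combined protocol and SAP*

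**What the plan says.** The table that identifies participants (Study procedures and methods, item 1.A) holds two kinds of field for each drug class. One is a recent-dispensing flag, for diabetes "Whether dispensing of a diabetes medicine was recorded during the last 2 months". The other is a single named product: "Name of (the last) diabetes medicine dispensed - with dose and quantity" and "Name of (the last) cholesterol lowering medicine dispensed - with dose and quantity". No count of medicines is listed, in either class or overall.

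For alert 2, the inclusion criteria require "dispensing diabetes medicines during the last 2 months". Alert 3 has the matching requirement for cholesterol-lowering medicines.

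Study Hypotheses, B, names as secondary outcomes "reduced number of dispensed anti-diabetes medicines" for the HbA1c% intervention and "reduced number of dispensed anti-cholesterol medicines" for the cholesterol intervention. Item 4 (c and d) collects the name, dose and quantity of class medicines over the three months after the email, without restricting this to the last one dispensed.

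Item 6, Outcome analysis, compares the arms by Chi-square or Fisher's exact test, or by "T-test (or Wilcoxon two sample test) for continuous variables". It mentions no baseline covariate.

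**The concern.** How many diabetes medicines a patient takes after the email is likely to depend on how many the patient took before it. An analysis that ignores the starting number leaves that between-patient variation in the error term. The flag cannot help: within the alert 2 and alert 3 groups it is constant by design. The last-dispensed field shows one medicine whether the patient takes one or more.

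Patients on more than one medicine are not a side issue for alert 2. Eligibility is not limited to one medicine, and the Background supports the alert with a U-shaped relation "with increased mortality under a 6.5% level in patients taking two antidiabetic medicines".

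At stake is the precision of two secondary comparisons. Mortality and the sample size are not touched.

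**Working it through.** **The plan's own figure.** The plan gives no precision or power figure for the medicine-count outcomes. Its only sizing statement (item 1.C: about 10,000 patients, deaths falling from 3% to 1.8%) concerns mortality and has no bearing here.

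**What the listed fields can supply**

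| Needed for a baseline count | Listed in item 1.A | Information in the alert 2 and 3 groups |
|---|---|---|
| Any class medicine in the last two months | Yes/no flag | None: yes for all by inclusion |
| Number of class medicines | Not listed | None |
| Identity, dose and quantity | Last-dispensed medicine only | One medicine, whatever the number taken |

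**Model for the gain.** All inputs are assumptions. The count is read as the number of distinct medicines, which the plan does not define.

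- Baseline count B is 1 or 2, with P(B = 2) = p.
- Each baseline medicine is still dispensed at follow-up with probability c.
- One medicine is added with probability a = 0.05.

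Given B, the expected follow-up count is cB + a, which is linear in B. The variance therefore splits into:

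- explained by B: E = c²p(1 − p)
- residual: R = (1 + p)c(1 − c) + a(1 − a), where a(1 − a) = 0.05 × 0.95 = 0.0475

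Adjusting for B removes the share r² = E / (E + R) of the variance of the arm difference. This is equivalent to multiplying the sample by 1/(1 − r²).

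Worked case, p = 0.10 and c = 0.8: E = 0.64 × 0.09 = 0.0576. R = 1.10 × 0.16 + 0.0475 = 0.2235. So r² = 0.0576 / 0.2811 = 0.205.

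**Alert 2, variance cut r²**

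| c | p = 0.10 | p = 0.30 | p = 0.60 | Largest for p from 0.10 to 0.60 |
|---|---|---|---|---|
| 0.5 | 6.5% | 12.4% | 11.8% | 13.1% |
| 0.6 | 9.4% | 17.4% | 16.7% | 18.4% |
| 0.7 | 13.7% | 24.3% | 23.5% | 25.7% |
| 0.8 | 20.5% | 34.5% | 33.6% | 36.2% |
| 0.9 | 33.2% | 50.8% | 50.4% | 53.0% |

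The largest values fall at p of about 0.42 to 0.44. For c from 0.5 to 0.7 the cut is 6.5% to 25.7%, an effective sample 1.07 to 1.35 times as large. For c from 0.8 to 0.9 it is 20.5% to 53.0%, or 1.26 to 2.13 times.

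**Alert 3, variance cut r²**

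| c | p = 0.02 | p = 0.05 |
|---|---|---|
| 0.5 | 1.6% | 3.7% |
| 0.7 | 3.5% | 8.0% |
| 0.8 | 5.6% | 12.4% |
| 0.9 | 10.2% | 21.3% |

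At p = 0, B is constant, E = 0 and the gain is zero.

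**In medicines per patient.** Assume 1,000 patients per arm (the documents give no alert-group sizes), 80% power and a two-sided 0.05 level. The detectable difference is (1.96 + 0.84) × √(2V/1,000), with V = E + R unadjusted and V = R adjusted.

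- p = 0.30, c = 0.9: V = 0.3346 gives 0.072; V = 0.1645 gives 0.051.
- p = 0.10, c = 0.8: V = 0.2811 gives 0.066; V = 0.2235 gives 0.059.

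**The case against.** The strongest reply is that no planned analysis needs the baseline count. The secondary hypotheses compare randomised arms, so a two-sample test on follow-up counts is valid without it. This stands in full. A reader might infer that the comparison is biased, but the listed fields are fixed before randomisation and are the same in both arms.

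Second, item 1.A is a screening list and visibly incomplete: it omits HbA1c, without which alert 2 patients could not be found. A field missing from the list may still have been extracted, and the same computer system probably still holds earlier dispensings. This also stands, and a reader should not infer that the information is lost. What remains is that item 6 names no adjusted analysis. Specifying one before outcomes are seen is stronger than adding it later.

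Third, other utilisation outcomes (stays, visits, expenses) have no listed baseline either. True, but here the query already reads the dispensing record, so the remedy is unusually cheap.

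Two further readings go beyond the documents. One is that the medicine count is the most direct measure of whether clinicians acted. The letters ask for a lower dose, which a count can miss, and Hypothesis A.1 defines compliance as a rise in the index itself. The other is that the alert 2 and alert 3 letters would name only one medicine and so misdirect the clinic. The last-dispensed field is the only listed field that could fill the blank, but the plan does not say which field does, and the blank does not limit the entry to one medicine. The recipients are the patient's own physician and clinic nurse, who are also asked to reassess treatment generally.

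**Conclusion.** The point holds as a minor matter of efficiency. No listed field gives a pre-email count of class medicines, and the planned tests on the medicine-count outcomes are unadjusted. These tests are sound but less precise than they could be.

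The size depends on two quantities the documents do not give: the share of patients on two medicines and the probability that a medicine is continued. Over the assumed ranges the alert 2 gain runs from slight to a halving of the variance. For alert 3 it is small to moderate, and possibly nil. If the outcome means the number of dispensings rather than of distinct medicines, these figures do not apply. Nothing here shows that the lost precision would change a conclusion.

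**What to change.** In item 1.A, extract every diabetes and cholesterol-lowering medicine dispensed in the two months before the email, with name, dose, quantity and date, from the system already being queried. In item 6, analyse the alert 2 and alert 3 medicine-count outcomes with a linear model of follow-up count on arm and pre-email count, in place of the unadjusted test. State whether the count is of distinct medicines or of dispensings.

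As an optional by-product, the same extract lets the medicine blank in Appendices 2 and 3 list all of the patient's current medicines in the class.

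The cost is low: several rows per patient in an existing query, one extra model for secondary outcomes and, if the option is taken, one combined mail-merge field. The downside is a wider table and slightly longer letters.
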